These are detections that could not be classified as a an obviously false positive at first sight and which is indicated by the endoscopists as a side that needs further inspection. In case this is not spotted by the endoscopists, the second observer will ask the endoscopists to perform a second or close-by inspection for better evaluation, not showing endoscopic evidence of a polyp

We subdivided this type of false positive detections in 3 subdivisions:

- 1) (Thickened) fold
- 2) Other: mucosal lesions different from normal colonic mucosa
- 3) Not relocated: the detection could not be relocated for additional endoscopic inspection
- (3) Other false positive detections

This is every other false positive detection that does not fit any other class and does not need a second or close-by inspection.

 True positive detection: The AI-tool detects a mucosal lesion that is endoscopically diagnosed to be a polyp at first sight (detected by the endoscopist) or after second and close-by look (if initially missed by the endoscopist).

If in case of doubt the endoscopist takes a biopsy to rule out a polyp, this detection will be considered as a true positive detection by AI.

Negative detections:

- False negative detection: Every polyp that is found by the endoscopist and is not detected by the AI tool before the attempt of endoscopic optical diagnosis. On detection of a polyp, the endoscopist will use a standardized verbal action (ask "Did the system detect the polyp as well?"), to inform the second observer about the detection. Immediately the second observer hits the detection button on the AI system. This is a button that initiates timelimited indicator on the AI coupled screen for 1 second. If no detection is made by the AI system during that time, the endoscopically found polyp is to be considered as a false negative detection for the AI system.

5. Endpoints

Primary endpoint

Total polyp detection during single pass colonoscopy by the artificial intelligence tool in comparison to polyp detection by the endoscopist with endoscopic diagnosis as a gold standard.

Secondary endpoints

- 1. Total polyp detection during single pass colonoscopy by the artificial intelligence tool in comparison to polyp detection by the endoscopist with histological diagnosis as a gold standard.
- 2. The number of extra detected polyps by artificial intelligence with the endoscopic diagnosis as a gold standard.

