- 3. The number of extra detected polyps by artificial intelligence with the histological diagnosis as a gold standard.
- 4. The endoscopist's polyp miss rate defined as the additional detection of polyps during colonoscopy
- 5. The false positive rate during clean withdrawal.

Exploratory endpoints

- 1. Correlation between the Boston Bowel Preparation Score and the number of false positive detections during colonoscopy.
- 2. Correlation between the endoscopist's historical adenoma detection rate and the number of extra detections and false negative detections by the artificial intelligence system.
- 3. Correlation between the polyp size and number of false negatives and additional detections.
- 4. Correlation between the Paris classification and the number of false negatives and additional detections.

- 5. Correlation between the total number of polyps per colonoscopy and additional detections.
- 6. Correlation between the experience of the endoscopist and additional detections.

6. Study Design

This is an investigator-initiated multicentre non-randomized prospective interventional trial to validate the performance of a novel state-of-the-art computer-aided diagnostic (CAD) tool in polyp detection implemented as second observer during routine diagnostic colonoscopy and to evaluate its feasibility in daily endoscopy. Consecutive patients referred for a screening, surveillance or diagnostic colonoscopy will be included. After standard bowel preparation with PEG based solutions, patients will undergo a standard colonoscopy performed by an endoscopist with moderate to high adenoma detection rate (ADR > 20% and < 50%). A second observer, who is not a trained endoscopist, but a person trained for recognition of polyps and endoscopic lesions (see section 8), will follow the procedure on a bedside AI-tool to count the number of detections made by the AI system and categorize the results into positive or negative results as follows (1) true positive, (2) false negative or (3) false positive (detailed description, see section 4).

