When a detection is made by the AI system and this detection can clearly be categorized the endoscopist and second observer do not communicate. In case of a detection of the AI-system that was not seen by the endoscopist or is unclear to the second observer, the second observer will ask to re-evaluate the indicated region to determine whether after second look it is a true positive not detected by the endoscopist or a clinically relevant false positive detection of the AI system since it caused the endoscopist to take an extra action. Endoscopists will inspect perform a standard colonoscopy with a single withdrawal, inspecting each segment only once, except when the second observer asks to reinspect a certain area in case of a clinically relevant AI detection. The different timings in each segment will be separately measured with a built-in chronometer in the artificial intelligence tool. Time measurement will be initiated once withdrawal is initiated in the caecum and will be determined for every specific segment. In case of therapeutic actions, time registration will be paused and restarted after completion of this therapeutic act. Automated time calculation is integrated in the AI system and provides an overview of the real withdrawal time and the performed therapeutic time. The entire procedure is recorded. The practical set-up is shown in figure 2.

[figure not shown]

Figure 2: Basic set-up of the computer-aided diagnostic (CAD) tool as second observer during endoscopy. A patient undergoes a diagnostic colonoscopy performed by an experienced endoscopist (ADR > 20% and <50%), while a second observer watches the by the CAD-analyzed video to count and categorize the indicated detections. There is no communication between the endoscopist and the second observer unless a clinically relevant finding is found by the second observer or a polyp or clinically relevant finding is made by the endoscopists.

7. Study Population

Inclusion criteria

- Age ≥40 years
- Referral for screening, surveillance or diagnostic colonoscopy
- Able to give informed consent by the patient or by a legal representative

Exclusion criteria for study inclusion

- <40 years old
- Referral for a therapeutic colonoscopy
- Known Lynch syndrome or FAP syndrome
- Any contraindication for colonoscopy or biopsies of the colon

- Uncontrolled coagulopathy
- Confirmed diagnosis of inflammatory bowel disease prior to the scheduled colonoscopy
- Short bowel or ileostomy
- Pregnancy

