- All SAEs must be followed up until the outcome of the event is 'recovered', 'recovered with sequelae', 'not recovered' (in case of death due to another cause) or 'death' (due to the SAE) and until all related queries have been resolved, or until end of trial (whichever occurs first).
- Non-serious AEs must be followed up until the patient's last study visit, and until all related queries have been resolved.

Pregnancy

Female subjects must be instructed to notify the Investigator immediately if they become pregnant during the trial. The Investigator must report any pregnancy in subjects during the trial to the Sponsor.

Death

All deaths will be reported without delay to the Sponsor (irrespective of whether the death is related to disease progression, study procedure or is an unrelated event). The sponsor will notify all deaths, as soon as possible after becoming aware, to the Central EC and the EC of the concerned site and provide additional information if requested.

Reporting requirements to Ethics Committee's (EC's) The Investigator is responsible for ensuring that all safety events are recorded in the (e)CRF and reported to the Sponsor in accordance with instructions provided below.

The Sponsor will promptly evaluate all SAEs and AESIs against medical experience to identify and expeditiously communicate possible new safety findings to Investigators and based on applicable legislation.

Annual reporting

The sponsor has the obligation to, once a year throughout the clinical trial (or on request), submit a progress report to the EC's containing an overview of all SARs occurred during the reporting period and taking into account all new available safety information received during the reporting period.

10. Statistical Consideration

Sample size calculation for a validation study on artificial intelligence in polyp detection. The aim is to compare the accuracy of the detection by AI versus the endoscopist.

- The accuracy by AI is assumed to be 97% (pilot data). The accuracy by the endoscopist in the study setting of university hospitals is assumed to be 95%.
- The sample size is the number of polyps needed with an average of 2 polyps per patient (pilot data)

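### A polyp first seen on an AI-prompted re-look, other than the prompted lesion, counts as an endoscopist find and an AI miss in a single-pass endpoint if the AI does not box it

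*Combined protocol and SAP*

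**What the plan says.** Section 5 defines the primary endpoint as "Total polyp detection during single pass colonoscopy by the artificial intelligence tool in comparison to polyp detection by the endoscopist", judged by endoscopic diagnosis. Secondary endpoint 1 is the same comparison judged by histology. Section 8 repeats that withdrawal is a single pass.

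Section 6 allows one exception: "inspecting each segment only once, except when the second observer asks to reinspect a certain area" after an AI detection judged clinically relevant. The second observer asks for it when the endoscopist has not seen an AI detection or when the observer cannot classify it. Some of these re-looks therefore end with no polyp at the indicated site, and the prompt is then logged as a clinically relevant false positive.

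Section 4 contains two attribution rules:

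- The prompted lesion. If it proves to be a polyp "after second and close-by look (if initially missed by the endoscopist"), it is an AI true positive.
- A polyp the AI does not detect. An AI false negative is "Every polyp that is found by the endoscopist and is not detected by the AI tool before the attempt of endoscopic optical diagnosis". The rule limits the time the AI has to respond. It does not say in which phase, first pass or prompted re-look, the endoscopist must have found the polyp.

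Secondary endpoint 4 is "The endoscopist's polyp miss rate defined as the additional detection of polyps during colonoscopy", which does not separate the phases either. The synopsis describes the miss rate as applying after a single pass.

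**The concern.** During a prompted re-look the endoscopist may notice a polyp that is not the prompted lesion and that neither reader picked up on the first pass. On a single-pass definition both readers missed it. Under section 4 it is scored differently:

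- **The AI does not box it in time.** It counts as an endoscopist find and an AI false negative. In the paired table it falls in the endoscopist-only cell, although the endoscopist returned to that area only because of the AI.
- **The AI boxes it during the re-look.** It is an AI true positive. The plan does not say whether the endoscopist saw it on first view or initially missed it.

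The AI intervention thus carries over into the comparator's score. The McNemar contrast rests on the discordant cells, and the planned margin is two percentage points, so a few polyps in the wrong cell matter. The same polyps enter the AI false-negative counts used in exploratory endpoints 2 to 4, and they leave the endoscopist miss rate ambiguous.

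**Working it through.** **Inputs from section 10.** AI accuracy 97%, endoscopist accuracy 95%, McNemar test, two-sided 5%, power 90%, 2084 polyps, 2 polyps per patient (2084 / 2 = 1042 procedures). The discordance rate is not stated. I assume that AI and endoscopist errors are independent.

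**Planned paired table.**

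- AI-only: 2084 × 0.97 × 0.05 = 101.1
- Endoscopist-only: 2084 × 0.95 × 0.03 = 59.4
- Net difference D = 101.1 − 59.4 = 41.7; total discordant S = 160.5

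**The plan's own figure.** With discordant proportions 0.0485 and 0.0285, exact two-sided McNemar power at 2084 polyps is 89.95%. The asymptotic formula without continuity correction needs 2019 polyps, and two continuity-corrected variants need 2069 and 2118. The stated 2084 is therefore consistent with independent errors.

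**Effect of k unboxed re-look polyps.** Each adds one endoscopist-only pair, so D falls by k, and S and n rise by k. Asymptotic power = Φ[(D − 1.96√S) / √(S − D²/n)].

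| k (assumed) | D | S | z | Power |
|---|---|---|---|---|
| 0 | 41.68 | 160.47 | (41.68 − 24.83) / 12.63 = 1.33 | 90.9% |
| 1.6 | 40.08 | 162.07 | (40.08 − 24.95) / 12.70 = 1.19 | 88.3% |
| 5 | 36.68 | 165.47 | (36.68 − 25.21) / 12.84 = 0.89 | 81.4% |
| 10 | 31.68 | 170.47 | (31.68 − 25.59) / 13.04 = 0.47 | 68.0% |

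**How large k might be.** The documents give neither the rate of prompted re-looks nor the yield of other polyps. As an illustration, assume 0.25 to 0.5 re-looks per procedure, of which 2% to 10% reveal another polyp: 1042 × 0.25 × 0.02 = 5, and 1042 × 0.5 × 0.10 = 52. Only the unboxed share changes the contrast. At the planned AI miss proportion of 3%, k runs from 0.2 (5 × 0.03) to 1.6 (52 × 0.03). To reach k = 5 out of 52, 5 / 52 = 10% must be unboxed; for k = 10, 10 / 52 = 19%.

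**Miss rate.** Section 5 gives no denominator. Taking all polyps as the denominator, the planned value is 2084 × 0.05 = 104.2 misses, or 5.0%. With 10 re-look polyps counted as finds it is 104.2 / 2094 = 4.98%. Counted as first-pass misses it is 114.2 / 2094 = 5.45%.

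**The case against.** The strongest reply is that the plan already deals with the main case. The lesion that prompts the re-look is an endoscopist miss by definition. A reader might infer that the re-look lets endoscopists recover their misses in general. The documents do not support that: only other polyps in the indicated region are affected, and obvious false positives cause no re-look.

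A reader might also infer that every such polyp is credited to the endoscopist. The false-negative definition supports this only for polyps the AI does not box. A boxed one is either concordant or unsettled. The AI analyses the same re-look video, so both readers get the second view.

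The size is also uncertain. At 3% unboxed, the illustrative range costs at most about 2.6 points of power (90.9% to 88.3%), and 5 unboxed polyps would require 5 / 0.03 = 167 incidental finds. This stands as a caution about size. Its weak point is that the 3% is an average over all polyps, whereas these were overlooked by both readers on the first pass. The documents give no AI miss proportion for that group.

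Finally, a reader might infer a risk of a false superiority claim. There is none from this source, because the error favours the endoscopist.

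Two practical points also hold. The case report form is not among the documents, so a phase field may exist, although section 8's description mentions none. The procedure is recorded on video, so the timing could be recovered, but no such review is planned.

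**Conclusion.** The gap is real and narrow. For an endpoint defined over a single pass, the false-negative rule scores against the AI any unboxed polyp, other than the prompted lesion, that is first seen on an AI-prompted re-look. For a boxed one, the endoscopist's status is undefined.

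The number of such polyps is unknown and probably small, and the bias is against AI superiority. Under independent errors, 1.6 of them would lower power from 90.9% to 88.3%, 5 to 81.4% and 10 to 68.0%. All three counts are assumptions. The lower figures require the AI to do clearly worse on these polyps than its planned 97%, or far more incidental finds than illustrated. The point deserves correction because the planned margin is about 42 polyps, the rule as written gives the wrong attribution, and a choice made after the data are seen would be open to challenge.

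**What to change.** 1. Add one case report form field per polyp with three options: first seen on the first pass; prompted lesion; other polyp first seen during a prompted re-look. The existing video can confirm the entry.
2. State in sections 4 and 5 that the third group is neither an endoscopist detection nor an AI false negative in the primary comparison and secondary endpoint 1. Leaving these polyps out and scoring them as missed by both readers give the same McNemar discordant counts. Choose one in advance, because the reported accuracies differ slightly.
3. Report the third group separately, split by whether the AI boxed the polyp.
4. Show the endoscopist miss rate (secondary endpoint 4) twice: with these polyps counted as first-pass misses, and without them. Dropping them alone would not repair the understatement.

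The cost is one tick box and a short addition to two sections, with no change to the procedure or to patient care. The downside is that a few polyps leave the primary count if they are excluded.

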Exclusion criteria for study analysis

- Colonic inflammation of > 30cm during colonoscopy
- Incomplete colonoscopy for any reason
- Incomplete recording or technical failure of the artificial intelligence system

8. Study Procedures

Bowel preparation

Before endoscopy patients will be prepared either at home either in hospital with standard bowel preparation according to local practice in the respective research centers, with an oral polyethylene glycol based regimen and if necessary, with an additional water enema. During endoscopy, all residual stools will be removed from the colonic wall by rinsing with water with or without dimeticon. Every subject's bowel preparation will be scored using the Boston Bowel Preparation Scale (BBPS).

Endoscopy, video recording

Endoscopy will be performed in patients on the scheduled appointment as initially made after selection based on referral. Video recording of the procedure will be initiated to record the patient's number upon the case report form before the endoscope is introduced in the anal canal. Before withdrawal, a picture of the caecum needs to be taken. During withdrawal the bowel should be as maximal inflated as possible for a high-quality inspection. A single pass withdrawal will be applied during inspection.

If a polyp is found, it can be resected after an endoscopist's optical assessment. This endoscopist's optical assessment should include description of the polyp size, location, Paris classification and if possible endoscopic diagnosis of most probable histology (hyperplastic, sessile serrated, adenoma or carcinoma).

If more than 5 polyps with apparent hyperplastic morphology are found in the rectosigmoid, the first 5 polyps will be included for analysis of the AI tool performance and will be resected for histological assessment and inclusion in the study. Any additional apparent hyperplastic polyps in the rectosigmoid exceeding the number of 5 will be discarded from the study for practical reasons. Most of these polyps will be hyperplastic and are clinically irrelevant. Additional separate biopsies of these sometimes many polyps will incur unnecessary costs. The entire procedure needs to be recorded as one video.

Second observer

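### The five-polyp cap on apparent hyperplastic rectosigmoid polyps removes detection data as well as histology, and can drop AI-only polyps somewhat more often than AI misses

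*Combined protocol and SAP*

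**What the plan says.** Section 8 (Endoscopy, video recording) limits apparent hyperplastic rectosigmoid polyps once more than five are found. The limit covers performance data as well as tissue: "the first 5 polyps will be included for analysis of the AI tool performance". For the remainder: "Any additional apparent hyperplastic polyps in the rectosigmoid exceeding the number of 5 will be discarded from the study for practical reasons". The section adds that most such polyps are of no clinical relevance, and that "Additional separate biopsies of these sometimes many polyps will incur unnecessary costs".

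The primary endpoint (section 5) compares AI detection with "polyp detection by the endoscopist with endoscopic diagnosis as a gold standard". Secondary endpoint 2, extra polyps found by the AI, uses the same standard. Histology is the standard only for secondary endpoints 1 and 3.

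The two readers' finds come to be counted by different routes (sections 4 and 6). A polyp found by the endoscopist counts when called, and the AI result is settled within a one-second window. An AI-only polyp takes a longer path, which section 6 opens with the words "In case of a detection of the AI-system that was not seen by the endoscopist or is unclear to the second observer". A prompt for re-inspection follows, and the polyp becomes a true positive only once that second look confirms it. The second look is an exception within the single withdrawal, which otherwise means "inspecting each segment only once, except when the second observer asks to reinspect a certain area in case of a clinically relevant AI detection".

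**The concern.** There are two linked problems.

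First, one rule governs two kinds of data. Biopsy cost is a reason to limit tissue sampling. It is not a reason to discard which reader saw a polyp. Low clinical relevance does not separate the sixth polyp from the first five either, since those are kept.

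Second, *first* is undefined. It could mean first seen, called, confirmed, resected, or first by position. If it means order found or confirmed, polyps sharing a view may be ranked partly by who detected them, because an AI-only polyp needs an extra step. Who detected the polyp is the outcome that the McNemar test compares, so inclusion could depend on outcome.

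The planned advantage is only 2 points (97% against 95%) and rests on a small number of discordant pairs. A selective loss of AI-only pairs would pull that difference down. It would also understate extra detections (secondary endpoint 2) and the endoscopist's miss rate (secondary endpoint 4).

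**Working it through.** **Inputs from section 10.** AI accuracy 97%, endoscopist 95%, McNemar test, two-sided 5%, power 90%, 2084 polyps, independence assumed (ICC 0.003).

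**Assumptions, not in the documents.** The discordant cells, the number of polyps per view, and the share f of analysed pairs that come from capped patients.

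**1. The plan's own figure.** With d the difference and s the total discordance,

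n = (1.96·√s + 1.2816·√(s − d²))² / d², with d = 0.02.

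- Independent readers: AI-only 0.97 × 0.05 = 0.0485, endoscopist-only 0.03 × 0.95 = 0.0285, s = 0.077. This gives n = 2019, or 2069 with continuity correction.
- No polyp missed by both: 92% both, 5% AI-only, 3% endoscopist-only, s = 0.08. This gives n = 2097.

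The stated 2084 lies within 3.1% of each, so it is reproduced approximately. Power at 2084 is Φ[(d·√2084 − 1.96·√s) / √(s − d²)] = 90.9% for s = 0.077 and 89.8% for s = 0.08. The 92/5/3 split is used below.

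**2. The first five in a capped patient.** Suppose that within each view the AI-only polyps are counted after the endoscopist-called ones. A completed view loses nothing. Selection occurs only in the view where the fifth place falls.

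- *Two per view.* The fifth place comes from a pair and is AI-only only if both are: 0.05² = 0.0025. AI-only share of the five: (4 × 0.05 + 0.0025)/5 = 4.05%. Endoscopist-only: (4 × 0.03 + 0.03 + 0.05 × 0.03)/5 = 3.03%. Difference 1.02 points.
- *Three per view.* Two places come from a view of three. Expected AI-only kept there: 3 × 0.05² × 0.95 + 2 × 0.05³ = 0.0074. AI-only: (0.15 + 0.0074)/5 = 3.15%. Endoscopist-only: (0.09 + 1.9926 × 3/95)/5 = 3.06%. Difference 0.09 points.
- *Four per view.* The fifth place is almost never AI-only. AI-only: 0.20/5 = 4.00%. Endoscopist-only: (0.12 + 3/95)/5 = 3.03%. Difference 0.97 points.
- *One or five per view.* The fifth polyp closes a view, so nothing is lost: 5% and 3%.
- *Eight or more, all in one view.* AI-only about 0%, endoscopist-only 3/95 = 3.16%. Difference −3.16 points.

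**3. Both kinds are dropped.** With ten eligible polyps, a patient has on average 0.5 AI-only polyps and 0.3 AI misses.

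| Polyps per view | AI-only dropped | AI misses dropped |
|---|---|---|
| 1 or 5 | 50% | 50% |
| 2 | 1 − 0.2025/0.5 = 59.5% | 1 − 0.1515/0.3 = 49.5% |
| 3 | 1 − 0.1574/0.5 = 68.5% | 1 − 0.1529/0.3 = 49.0% |
| All in one view | about 100% | 1 − 0.1579/0.3 = 47.4% |

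**4. Effect on the primary comparison.** Overall cells are (1 − f) × (5%, 3%) + f × (shares in step 2), put into the power formula at n = 2084.

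| Polyps per view | f = 2% | f = 5% | f = 10% |
|---|---|---|---|
| 2 | 1.98 points, 89.3% | 1.95, 88.5% | 1.90, 87.1% |
| 3 | 1.96, 88.8% | 1.90, 87.2% | 1.81, 84.0% |
| 4 | 1.98, 89.3% | 1.95, 88.4% | 1.90, 86.9% |
| All in one view | 1.90, 86.9% | 1.74, 81.5% | 1.48, 69.6% |

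**5. A second model.** This simulation used independent readers (4.85% and 2.85%).

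- *Immediate second look:* drop rates are equal (six polyps: 16.7% of AI-only, 16.6% of AI misses; ten polyps: 50.0% and 49.9%), the difference stays at 2 points, and power is unchanged.
- *Each AI-only polyp counted one place late:* 32.5% of AI-only against 15.8% of AI misses are dropped with six polyps, and 59.5% against 49.4% with ten. Power goes from 90.9% to 89.7% at f = 5% and 88.4% at f = 10%.

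**The case against.** The cap is a declared choice with stated reasons, and it applies to polyps whoever found them. Nothing makes the second observer's prompt wait until the endoscopist has called everything in view. An AI-only polyp confirmed in the sigmoid is counted before any polyp reached later in the rectum. If the second look is immediate, the cap is neutral. The rule acts only in patients with more than five such polyps, while the planned average is two polyps of all types per patient, so few pairs may be affected. Any bias runs against the AI and cannot manufacture a claim of AI superiority.

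All of that stands, and it limits the point. A reader might infer that AI-only polyps are always confirmed last and dropped while AI misses stay. The documents do not support this: the timing of the second look relative to other calls is not fixed, and step 3 shows AI misses being dropped in large numbers in every scenario. A reader might also infer a serious loss of power. The 81.5% and 69.6% figures require every polyp in a single view, every AI-only polyp ranked last, and a capped share of 5% or 10% that the documents do not give.

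What the objection does not answer is that the cost reason has no bearing on endpoints needing no tissue, and that an undefined *first* leaves room for inclusion to depend on the reader.

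**Conclusion.** The point holds in a limited form. The protocol discards detection data for a reason that concerns histology, and orders polyps by an undefined *first* that can, on one reasonable reading, disfavour AI-only polyps in capped patients.

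With two to four polyps per view and capped patients supplying 2-10% of pairs, the expected difference falls from 2.0 to about 1.8-1.98 points, and power from about 90% to about 84-89%. With an immediate second look there is no effect. Larger losses need all polyps in one view. These sizes rest on the assumed 92/5/3 split, the assumed clustering by view and the assumed capped share.

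The consequence is a probably small bias against the AI in the primary comparison, with matching understatement of extra detections and the miss rate. It does not raise the risk of a false AI superiority claim. It is worth correcting because correction is cheap and the planned margin is narrow.

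**What to change.** Leave the five-polyp limit on resection and histology unchanged. For endpoints based on endoscopic diagnosis, have the second observer also record the reader result (both, AI only, endoscopist only) for polyps beyond the fifth. Report the primary comparison, extra detections and miss rate with and without those polyps.

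If a cap is kept for the primary analysis, define *first* by a criterion unrelated to the detector, such as anatomical position. Numbering by the earlier of the AI box and the endoscopist's call looks neutral but is not. If boxes precede calls, AI misses rank last within a view. With ten polyps in one view, endoscopist-only pairs fall to about 0% and AI-only pairs rise to 5/97 = 5.2%, which favours the AI in a superiority test.

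The cost is a wording change in the protocol and CRF, one sensitivity analysis, and a few more marks per affected procedure. The second observer already counts every AI detection on withdrawal, and the whole procedure is recorded. No extra biopsies are needed. The one statistical drawback is larger clusters from a few patients, confined to the sensitivity analysis.
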